## 2. LAY SUMMARY

There are 50,000 people who develop breast cancer each year in the United Kingdom, mostly women after their menopause and of a type known as oestrogen-receptor positive, HER-2 negative (human epidermal receptor-2). The current usual standard treatment is surgery within a month of diagnosis, followed by radiotherapy for some where required, and anti-hormone therapy (known as endocrine therapy) for 5-10 years. Most post-menopausal patients with early breast cancer will not require chemotherapy. Almost one half will be treated by surgical removal of the breast (mastectomy). For others, lumpectomy (breast conservation surgery), will ensure that a limited amount of breast tissue is removed at surgery.

Endocrine therapy after surgery is very effective in the long-term treatment of breast cancer; it is however currently unknown whether it is also beneficial to start this same endocrine therapy before surgery, known as neo-adjuvant endocrine therapy (NET). This study is to determine whether giving some of the endocrine therapy before surgery will shrink the tumour prior to operating. This could increase the rates of breast preservation by reducing the number of mastectomies for some women and the extent of surgery for others (removing less tissue leaves less defect).

After mastectomy many patients do not want or are unsuitable for breast reconstruction. Even if received, this may not always fully compensate for breast removal. If it is shown that NET reduces the amount of breast tissue that has to be removed and increases the rates of breast preservation, this would be anticipated to improve cosmetic outcomes, leading to better quality of life. This study therefore compares the traditional order of surgery within a month, to a period of treatment with endocrine therapy followed by surgery.

Participants in this randomised controlled trial are allocated by chance to one of two arms, which determines their treatment schedule. Endocrine therapy is usually started after surgery. However, all participants in both trial arms will start endocrine therapy (letrozole, anastrozole or exemestane) on joining the trial and prior to surgery. Therefore, they may have the opportunity to start treatment with endocrine therapy before they normally would. If patients start aromatase inhibitor endocrine therapy following their current diagnosis of breast cancer as part of routine care before the trial, this is allowed provided the endocrine therapy was not started more than 14 days prior to trial entry.

Participants in both arms have endocrine therapy for the same total length of time within the trial, but it is the timing of the surgery that differs. The type of surgery all participants will have will be determined by them and their clinical team as part of standard clinical care. Arm 1 will have surgery within 2-4 weeks (up to 8 weeks permitted for trial purposes) of starting their pre-surgical endocrine therapy; arm 2 will receive surgery after 6 months (+/-1 month) of pre-surgical endocrine therapy (neoadjuvant endocrine therapy;

EndoNET\_Protocol\_V4.0\_21Aug2024

© Copyright: The University of Oxford and Oxford University Hospitals NHS Foundation Trust 2022 Page 11 of 84 NET). Participants in Arm 2 will receive an ultrasound (USS) scan at 3 months and 5 months to closely monitor their response to this endocrine therapy prior to their surgery.

Patients with breast cancer, included as part of the study leadership team, and others have been extensively consulted in the trial design. They indicated preserving the breast and overall quality of life as the most important outcomes by which to measure study success.

The trial aims to recruit at least 792 women from at least 30 NHS hospitals across the UK. Participants in both arms will have their surgical treatments recorded and will complete quality of life questionnaires at intervals during their 15-month participation in the study. The results will be published in medical journals and presented at international conferences and updates of study progress will be available on the website and by study newsletter.

As part of this research, we are also running sub-studies to which patient participation is optional:

- The 'Information study', called the QuinteT Recruitment Intervention study, will investigate the different factors that can affect patient participation in EndoNET. This is being led by researchers at the University of Bristol.
- The 'Nested Qualitative Study' will investigate the experiences of participants in the main trial. Specifically, it will focus on how well they have tolerated their endocrine therapy and how this and their other breast cancer treatments have affected their quality of life.

## 3. SYNOPSIS

Trial Title	Randomised controlled trial evaluating effectiveness of neoadjuvant		
	endocrine treatment in post-menopausal women (EndoNET)		
Internal ref. no. (or	EndoNET		
short title)			
Trial registration	EudraCT number: 2022-000582-40		
	ISRCTN number: ISRCTN11896599		
Sponsor	University of Oxford		
	Research Governance, Ethics and Assurance (RGEA)		
	Joint Research Office		
	[name]		
	[name]		
	Headington		
	[name]		
	[contact]		
	Email: [contact]		
Funder National Institute for Health Research			
	Health Technology Assessment Programme		
Clinical Phase	Phase III		
Trial Design	EndoNET is a prospective, phase III, multicentre randomised controlled		
	trial (RCT).		
	Patients will be randomised 1:1 to either the intervention (NET) arm (6 +/-		
	1 months of NET followed by surgery and adjuvant ET) or the control arm		
	I months of the followed by surgery and adjuvant ery of the control and		

EndoNET\_Protocol\_V4.0\_21Aug2024 © Copyright: The University of Oxford and Oxford University Hospitals NHS Foundation Trust 2022 Page 12 of 84

	(2-4 weeks of presurgical ET and surgery within 2-4 weeks [up to 8 we permitted for trial purposes] followed by adjuvant ET).		
	Both arms will receive the same treatments (surgery, ET, and radiotherapy where indicated), but the sequencing of surgery will differ; both arms starting ET at randomisation*, with 6 months +/- 1 month of the course of ET delivered prior to surgery in the NET arm.		
	*Some patients may have already started aromatase inhibitor endocrine therapy as part of their standard of care.		
Trial Participants	Post-menopausal women with strongly ER+, invasive breast cancer where chemotherapy or anti-HER-2 therapy is not planned or has not started		
Sample Size	Main Trial: We will recruit a maximum of 1060 (for 90% power), with a minimum of 792 (for 80% power) post-menopausal women with strongly ER+, invasive breast cancer who are not planned or have not started chemotherapy or anti-HER-2 therapy		
	QRI 'Information study' (optional sub-study):		
	Approximately 50 audio-recordings of patient recruitment discussions (a eligible patients to be approached for the duration of recruitment period		
	Approximately 30 interviews with clinicians or researchers involved in trial recruitment.		
	Nested qualitative study (optional sub-study):		
	Approximately 60 qualitative interviews with participants.		
Planned Trial Period	The overall period of the trial is 69 months with an end date of 28/02/2027 including:		
	6 months set-up, 42 months recruitment, 15 months follow-up and 6 months data analysis and final reporting of results.		
	A formal stop/go review took place on 31 st December 2023. A second review is planned in December 2024.		
	Participants will also be asked to give consent for the collection of routine NHS data for long-term follow up. This may be for a period of, for example, 20 years or more, subject to receipt of suitable funding and/or resources and submission via a substantial amendment.		
Planned Recruitment	42 months		
period			

	Objectives	Outcome Measures	Timepoints
Primary	The overall aim is to evaluate whether 6 (+/- 1) months of NET reduces surgical burden resulting in a higher proportion of breast conservation in post- menopausal women with ≥15mm, strongly ER+ invasive breast cancer who are not planned or have not started chemotherapy or anti-HER-2 therapy 	Proportion of patients who have breast conservation (surgery)	15 months post- randomisation
Secondary	
 
To evaluate whether 6 months of NET results in better HRQoL over 15 months 
 
	
 
Difference in global HRQoL (as measured by FACT-B)
 
	
 
Baseline, 6 weeks or post-operative, 5 and 15 months post- randomisation
 

	
 
To evaluate tumour response rates following NET
 
	
 
Response rates according to RECIST (USS, clinical, relative to baseline); MRI where used as part of local unit centre policy
 
	
 
2-4 weeks, 3 and 5 months post- randomisation (NET arm)
 

	
 
To compare invasive tumour size, histological grade and lymph node status (including number of involved nodes) in both arms 
 
	
 
Tumour size, histological grade and lymph node status pre-surgery and final histology post-surgery
 
	
 
Pre and post- operative
 

	
 
4. To compare, in both arms, the HRQoL related to body image and surgery (FACT-B with ES and +4, Breast Q, EQ-5D-5L, Hopwood Body Image Scale [BIS])
 
	
 
Patient reported outcomes as measured by FACT-B (with ES and +4), Breast-Q, Hopwood Body Image Scale and EQ-5D-5L
 
	
 
Baseline, 6 weeks or post-operative, 5, 7, and 15 months post- randomisation
 

5	5. To provide an estimate of the risk of relapse and measure of endocrine sensitivity in NET arm 	5. Pre-operative Endocrine Prognostic Index (PEPI) score	
 
Baseline sample,
 
2-4 week sample and post- operative sample
 

6		6. Post-surgical Complications, side effects; delays to commencement of subsequent treatment	
 
6. 2-4 and 6 weeks,
 
3 months, 5, 7, 12 and 15 months
 
post-randomisation
 

7		7. Treatment Compliance and rates of cross-over	
 
2-4 weeks, 5 months and 15 months post- randomisation.
 

8	
 
To evaluate the prognostic significance of Ki67
 
	8. Ki67 % in tumour cells, % reduction in Ki67 from baseline to biopsy or surgery	
 
Baseline (both arms) and after 2- 4 weeks of AI (in both arms) and at surgery (in comparator arm)
 

g	D. To assess the surgical and locoregional management of the breast 	9. Rates of re-excision and further surgery after BCS; specimen weight after BCS; requirement for advanced BCS (therapeutic mammoplasty and local perforator flaps), rate of reconstruction postmastectomy, breast radiotherapy	9. Baseline, post- operative, 15 months post- randomisation
1	0. To assess the surgical and locoregional management of the axilla 	10. Rates of sentinel node biopsy, axillary clearance, axillary radiotherapy	10. Baseline, post- operative, 15 months post- randomisation
1	1. To compare rates of local and distant recurrence 	11. Rates of local and distant recurrence	
 
11. 15 months post- randomisation, and periodically for long term follow up 
 

1	2. To compare breast cancer specific survival in both arms 	12. Breast cancer specific and overall survival	12. 15 months post- randomisation and periodically

			for long term follow up 
	13. To assess the cost- effectiveness of implementing NET followed by surgery and adjuvant ET compared with the current practice of surgery followed by adjuvant ET for reduction in mastectomy (Health Care Use Questionnaire) 	13. Resource utilisation, cost and cost- effectiveness of implementing NET followed by surgery and adjuvant ET compared with the current practice.	13. Baseline, 6 weeks, 7 months and 15 months post randomisation
	
 
14. To compare accuracy of Ultrasound (USS) and MRI (where available) for assessment of initial extent of disease and for detection of tumour response, using these two different imaging modalities 
 
	14. Accuracy of USS (and MRI where available) to determine conversion to BCS	14. Up to 15 months post- randomisation
	15. To compare the requirement for adjuvant chemotherapy in both arms 	15. Number of patients receiving adjuvant chemotherapy in both arms	15. At 15 months
Intervention • IMP(s)		IMP: Pre-surgical (Neoadjuvant) Endocrine Therapy (aromatase Inhibitors, AI): letrozole, anastrozole or exemestane) following trial entry to surgery, in both arms: In intervention arm 6 (+/-1) months and control arm 2-4 weeks (up to 8 weeks permitted for trial purposes).	
		Choice of AI is according to cen letrozole (2.5mg/day), ana exemestane (25 mg/day).	tre policy and may be either astrozole (1mg/day), or

Comparator	Surgery within 2-4 weeks of trial entry ; up to 8 weeks permitted for trial purposes – either BCS or mastectomy +/- reconstruction followed by adjuvant therapy, including adjuvant ET.
	This is consistent with current best standard of care in the majority of patients where surgery takes place within the NHS 31-day time to treatment target.

 Outcomes within objective are measured in both the intervention (NET) and control arm.

Outcomes within objective measured in intervention (NET) arm only.

 Breast-Q administered at baseline and 15 months only. EQ-5D-5L administered at baseline, 6 weeks, 7 months and 15 months only. Hopwood BIS administered at baseline, 5 months and 15 months only. FACT-B with ES and +4 administered at baseline, 6 weeks, 5 months and 15 months. Refer to schedule of trial procedures in Section 9.2.

These are secondary objectives that will be assessed subject to additional funding and/or resources at 5, 10 and 20 years of EndoNET trial long-term follow up. Patients will be consented for long term follow-up on EndoNET trial entry.

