#### 5.4. Radiological response to NET

Ultrasound (USS) is available at all UK breast cancer centres and has therefore been selected as the primary modality to monitor response during the study. In the NET arm, in case of complete clinical response, a marker clip will be inserted under USS control between 2-4 weeks. The clip used to mark the biopsy/tumour location should be Conformité Européenne (CE) marked for this purpose. The opportunity will be taken at this timepoint to also provide a core biopsy sample for Ki67 to evaluate if this can be utilised as an early marker of NET response. USS will also be performed after 3 months and 5 months of NET treatment, to assess for continuing response to treatment. Our Patient and Public Involvement (PPI) consultation suggested that this would be important and requested close monitoring in NET arm to give participants confidence of continued response. Visibility of the tumour on USS is therefore one of the study inclusion criteria.

Not all centres will routinely utilise breast MRI in a NET setting. MRI is the most accurate imaging modality for delineating extent of disease and accurately determining response to treatment following NAC (58) and is useful in surgical planning. However, there is evidence for the value of MRI to assess response to NET (98), therefore a pragmatic sub-study analysis will be performed comparing accuracy for detection of initial extent of disease and for detection of response, using these two different imaging modalities where available.

EndoNET\_Protocol\_V4.0\_21Aug2024

© Copyright: The University of Oxford and Oxford University Hospitals NHS Foundation Trust 2022 Page 26 of 84 For the study endpoints radiology reports will be used as the study source material, however linkedanonymised radiological images may be collected and used for future research purposes subject to further funding and governance approvals. The exact process and location of storage will be specified in a subsequent substantial amendment prior to this occurring.

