## 9.9. Trial imaging (Main Trial)

## 9.9.1. Imaging for trial purposes

USS +/- breast MRI, are used in most centres to monitor response to preoperative neo-adjuvant treatment. In the NET arm USS is required 2-4 weeks after start of treatment in order to place the marker clip and take core biopsies for Ki67 measurements. USS is then required at 3 and 5 months to evaluate any possible tumour response to the AI. If a patient has dense breasts or a discrepancy between mammography and USS size estimates a baseline MRI is undertaken to assess disease extent. If local policy, the participant may have MRI at the follow up timepoints (e.g. at 3 and/or 5 months) to correspond to the USS evaluation. If breast MRI is standard practice for neo-adjuvant treatment at a centre then this may be used in this trial, in addition to USS.

Baseline USS examination should include examination of the whole breast to assess disease extent. The tumour is measured in at least two dimensions (usually perpendicular to each other) and documented in millimetres with the accurate position of the probe recorded and images archived to improve interobserver accuracy. In line with standard practice, the maximum tumour diameter will be recorded and used to assess tumour response using RECIST 1.1 criteria (102). It is advised that for the 3 and 5 month USS in the NET arm, that the radiologist should review any previous image(s) in order to try and replicate the same measurement planes to minimise the subjective bias in USS. It is also recommended that USS images are captured in both planes. This will also allow for use in future research.

The axilla should be assessed carefully prior to entry to the trial by USS (as per national guidelines for all patients with invasive breast cancer) with any abnormal nodes biopsied by core biopsy or fine needle aspiration cytology (FNAC). The number of abnormal nodes should be recorded and documented. USS guided core biopsy and marker clip insertion is undertaken at 2-4 weeks. Prior to biopsy the tumour size is measured taking care to use the same positioning as the baseline examination.

EndoNET\_Protocol\_V4.0\_21Aug2024

© Copyright: The University of Oxford and Oxford University Hospitals NHS Foundation Trust 2022 Page 48 of 84 MRI examinations if undertaken should follow local protocol.

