## 9.13. Subsequent Follow Up Visits

All follow-up visits in the standard of care comparator arm are in line with routine clinical practice with surgery by 2-4 weeks (up to 8 weeks permitted for trial purposes), as per NHS treatment targets.

In the NET arm, there are additional visits for USS with core biopsy and marker clip at 2-4 weeks and for USS and clinical assessment at 3 months and 5 months. Assessment timings are designed to correspond to routine care visits and ensure that, wherever possible, patients are assessed at comparable timepoints in the care-pathway in both arms.

Participants will complete questionnaires electronically and be emailed HRQoL and Health Care use questionnaires via REDCap at baseline, 2-4 weeks, 6 weeks, 5 months, 7 and 15 months, with an option to be contacted by the Surgical Intervention Trials Unit (SITU) by posted letter with a paper version of the questionnaires, if the participant expresses this as their preference. Participants may be contacted by telephone for any outstanding PROMs/questionnaires. In some circumstances, where it is not feasible to complete questionnaires using our preferred method(s), participants may complete questionnaires over the telephone. This may be due to a patient being located in a remote geographical location. Participants may be contacted by the central trial team to query any overdue data.

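### Outcome 14 scores ultrasound and MRI against conversion to BCS, which is neither what objective 14 asks about nor independent of the scans; final histological size should be the reference

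*Protocol*

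**What the plan says.** In the Protocol, section 3 (Synopsis) and the table in section 6.2, objective 14 is to compare the accuracy of ultrasound and MRI "for assessment of initial extent of disease and for detection of tumour response, using these two different imaging modalities". Section 5.4 describes the same sub-study as "comparing accuracy for detection of initial extent of disease and for detection of response, using these two different imaging modalities where available". The outcome measure in that row is "Accuracy of USS (and MRI where available) to determine conversion to BCS", and a footnote marks the row as measured in both arms.

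Section 5.4 says ultrasound was "selected as the primary modality to monitor response during the study" and that MRI "is useful in surgical planning". It also makes routine radiology reports the source for imaging endpoints. Section 9.7 says blinding is not possible. Section 9.10 leaves mastectomy or conservation to local and national guidance and to agreement between surgeon and patient.

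On who is scanned, section 9.9.1 says "If a patient has dense breasts or a discrepancy between mammography and USS size estimates a baseline MRI is undertaken", and section 9.9.2 repeats the trigger for preoperative MRI. MRI at 3 and 5 months follows local policy. Section 9.13 says that in the NET arm "there are additional visits for USS with core biopsy and marker clip at 2-4 weeks", with further ultrasound at 3 and 5 months. Outcome 3 already collects "Tumour size, histological grade and lymph node status pre-surgery and final histology post-surgery".

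**The concern.** An accuracy study needs a reference that measures the target condition and is obtained independently of the tests. Conversion to BCS meets neither requirement. Type of operation is not disease extent or response. A woman whose shrinkage was measured perfectly but who prefers mastectomy would count as an imaging error. Because surgeons see the scans before choosing the operation, part of the agreement between scan and operation is the scan agreeing with itself (incorporation bias).

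What is at stake is the interpretation of one secondary outcome. A reported sensitivity and specificity, and a ranking of ultrasound against MRI, would be read as diagnostic performance when they partly reflect how surgeons use each scan and what patients choose.

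**Working it through.** The protocol states no accuracy figure or sample size for outcome 14, so there is no figure to reproduce. The check sets the passages side by side and then uses assumed values to show what a dependent reference can do.

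**Objective against measure.**

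| Element | Extent | Response | Conversion to BCS |
|---|---|---|---|
| Objective 14 (sections 3, 6.2) | yes | yes | no |
| Section 5.4 | yes | yes | not as the accuracy target |
| Outcome 14 (sections 3, 6.2) | no | no | yes |

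**Arms.** Baseline ultrasound and triggered MRI are described for both pathways (9.9.1, 9.9.2), so the both-arms footnote is right for extent. Response imaging is scheduled only in the NET arm (9.9.1, 9.13), and outcome 2, tumour response, is itself marked NET arm only. The footnote is therefore wrong for the response limb.

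**Dependence of the reference (all inputs assumed).** Let 60% of women be truly suitable for BCS. Take ultrasound as truly 80% sensitive and 80% specific and MRI as 90% and 90%, with independent errors. Let *w* be the share of operations that simply follow one scan, the rest following the truth.

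For ultrasound, the shares of women are 0.48 (suitable, read suitable), 0.12 (suitable, read unsuitable), 0.08 (unsuitable, read suitable) and 0.32 (unsuitable, read unsuitable). If operations follow ultrasound with *w* = 0.5:

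- BCS share = 0.48 + 0.5×0.12 + 0.5×0.08 = 0.58; mastectomy share = 0.42.
- Apparent ultrasound sensitivity = (0.48 + 0.04)/0.58 = 89.7%; specificity = (0.32 + 0.06)/0.42 = 90.5%.
- Apparent MRI sensitivity = (0.9×0.54 + 0.1×0.04)/0.58 = 84.5%; specificity = (0.9×0.36 + 0.1×0.06)/0.42 = 78.6%.

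Apparent sensitivity/specificity (%) over the range:

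| *w* | Follow USS: USS | Follow USS: MRI | Follow MRI: USS | Follow MRI: MRI |
|---|---|---|---|---|
| 0 | 80.0/80.0 | 90.0/90.0 | 80.0/80.0 | 90.0/90.0 |
| 0.25 | 84.7/85.4 | 87.3/84.1 | 79.0/77.8 | 92.4/92.6 |
| 0.5 | 89.7/90.5 | 84.5/78.6 | 78.0/75.6 | 94.9/95.1 |
| 0.75 | 94.7/95.3 | 81.6/73.3 | 76.9/73.5 | 97.4/97.6 |

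At *w* = 0.5 and above, the better test ranks second on both measures if operations follow ultrasound. If they follow MRI, its lead is exaggerated.

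Patient preference can push the other way. With *w* = 0, suppose 20% of suitable women choose mastectomy regardless of the scan. The mastectomy share is 0.4 + 0.2×0.6 = 0.52, and apparent ultrasound specificity falls from 80% to (0.32 + 0.2×0.12)/0.52 = 66.2%.

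**Selection into MRI (extent limb, inputs assumed).** Let mammography be 75%/75%, ultrasound and MRI both 80%/80%, errors independent. If MRI is done only when ultrasound and mammography disagree, then among suitable women the selected share is 0.8×0.25 + 0.2×0.75 = 0.35. Ultrasound sensitivity in that subset is 0.20/0.35 = 57%, while MRI stays at 80%; specificity behaves the same way. If 20% or 50% of women also get MRI routinely, ultrasound reads 67% or 74%; with MRI in everyone it reads 80%. With uninformative mammography (50%/50%), the triggered subset gives 0.40/0.50 = 80%, with no distortion. The effect thus depends on quantities the protocol does not give.

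**The case against.** Conversion to BCS is a sensible thing to predict. BCS is the primary endpoint, the baseline surgical indication is recorded for minimisation (section 9.6), and section 5.3 treats Ki67 as a possible predictor of response or conversion. Read as prediction, outcome 14 has meaning. That stands, and it is a reason to keep the measure under its own label. It does not make conversion a reference for extent or response.

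Section 12.2 defers secondary methods to the SAP. Pairing of scans and stratification by reason for MRI could properly be settled there, so their absence from the protocol is no fault. The reference itself, however, is named in the protocol's outcome table and does not match its own objective.

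A reader might go further and infer three things that the documents do not support:

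- **That the comparison is tilted against ultrasound, or that accuracy must look high.** Ultrasound is the main monitoring tool, so dependence could favour it, and patient preference can lower apparent accuracy. The net direction is unknown.
- **That women with MRI are enriched for ultrasound failures.** The trigger is breast density or a mammography-ultrasound size discrepancy. Density is not an ultrasound result, and a discrepancy does not say which modality erred. The trigger applies to baseline or preoperative MRI; follow-up MRI, nearest to conversion, follows local policy.
- **That the both-arms label is simply wrong.** It is right for initial extent.

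Histology is not a perfect reference either, as the fix sets out.

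**Conclusion.** The point holds. As fixed in the protocol, outcome 14 does not measure what objective 14 and section 5.4 ask for, and its reference is not independent of the imaging being judged. Following it as written could give misleading accuracy figures and a misleading ranking of modalities. The percentages in the working rest entirely on assumed prevalence, accuracy, follow rates and independent errors. They show that bias of either sign is possible and do not estimate it for this trial.

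Selection into MRI is a narrower problem, bearing mainly on initial extent, and the footnote needs correcting only for response. This is one of 15 secondary outcomes, in what section 5.4 calls a pragmatic sub-study. The primary endpoint and the sample size of 792 to 1060 are untouched. The change is worth making before any comparative analysis, because it alters a stated outcome.

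**What to change.** 1. Reword outcome 14 so that invasive tumour size on final surgical histology (outcome 3) is the accuracy reference. Use baseline or preoperative imaging against histology in the control arm for extent, and the last pre-surgical imaging against histology in the NET arm for residual size.
2. State the limits. Control patients take an AI for 2-4 weeks (up to 8) before surgery, so histology is not a clean measure of baseline extent. Surgery at 6 (+/-1) months follows the 5-month scan by nominally 0 to 2 months. Histology gives residual size, not change.
3. Keep conversion to BCS as a separately labelled prediction or agreement measure in NET-arm women whose baseline indication was mastectomy.
4. Correct the footnote: both arms for extent, NET arm only for response or residual size.
5. Compare modalities in women who had both scans, reporting routine-policy MRI and triggered MRI separately, with the routine-policy group as the main comparison.

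The cost is wording in the two outcome tables and the SAP, one recorded item for the reason for MRI, and a smaller main comparison set. No extra scans or visits are needed, and the indications for imaging do not change.
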